3.8 Angiographic Imaging

At screening, perform a DSA to define the angio-architecture of the occluded vascular segment. While a DSA to define the angio-architecture of the occluded vascular segment is preferred, CTA or MRA is an acceptable substitute.

When possible, an assessment of collateral blood flow by DSA should be done per institutional standard of care, particularly in cases of terminal internal carotid artery occlusion.

Prior to mechanical thrombectomy by the Penumbra Device, obtain a baseline TIMI/TICI scores by DSA. CTA or MRA is not an acceptable substitute for this assessment. The investigator shall make an initial assessment of TIMI/TICI flow in the target vessel territory.

TIMI/TICI scores are to be assessed after completion of the procedure by the Separator 3D. If necessary, other components of the Penumbra System can be used at the discretion of the investigator with the TIMI/TICI scores recorded before and after each use. In the event that adjunctive treatments were used, TIMI/TICI scores should be assessed and recorded before and after each treatment. The TIMI/TICI scores after the use of the Penumbra System as well as after adjunctive treatments will be used for analysis.

Pre-procedure and post-procedure angiograms shall be sent to an unbiased Core Laboratory blinded to treatment allocation to make a final determination on TIMI/TICI flow.

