3.9 Adjunctive Therapies and Protocol Deviation

If the Penumbra System with Separator 3D or the Penumbra System alone is unable to revascularize the target vessel to TIMI/TICI 2 or 3, use of other rescue therapies are considered a protocol deviation and must be reported in the Case Report Forms. Any use of IA tPA or other non-FDA-approved treatments for the purpose of reducing the clot burden will be considered a treatment failure. TIMI/TICI scores must be recorded before and after the use of rescue therapy.

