3.4 Blinding

The Penumbra Inc. clinical team responsible for the conduct of the study, the investigator, and center study personnel will not be blinded to each patient's randomized treatment group throughout the course of the study. The study subjects and the Core Laboratory will be blinded to treatment assignment.

4 Interim Analysis

No interim analyses are planned for the purpose of stopping the study early.

5 Analysis Populations

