5.1 Definitions

All primary and secondary effectiveness endpoints will be performed for both the intent-to-treat (ITT) population and per-protocol (PP) population.

The ITT population will consist of all patients who signed the informed consent and are randomized in the study. The data from the ITT population will be analyzed by the treatment group assignment given at the time of randomization, even if the subject does not receive the correct treatment, or does not follow the protocol until completion. All randomized patients will

be followed and assessed for 90 days post-procedure, even when no neurothrombectomy is performed.

For the PP analysis, only patients who actually received the assigned treatment and do not have major protocol violations will be included.

For the safety analysis, patients will be analyzed according to the treatment they received.

Any treated patients who are not randomized through the IVRS system will be excluded from all analyses. The reason(s) for their exclusion from the study will be recorded. Listings will be provided for these patients, and they will be discussed in the clinical report.

Roll-in patients will be followed for 90 days and their safety will be summarized separately in the clinical report.

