9.1 Primary Effectiveness Analysis

The primary effectiveness variable is the proportion of patients with a post procedure TICl score of 2 to 3. The proportion of patients in each group who are successful based on this criterion will be calculated. The Core Laboratory data supersede the investigator-reported data in all analyses of TICl scoring.

For those patients who are treated with IA tPA or other non-FDA-approved treatments for the purpose of reducing the clot burden, their TICl score will be analyzed as a treatment failure (i.e. TICl 0 to 1) for the primary effectiveness analysis.

The primary effectiveness analysis will be the difference between the Penumbra System only group (control) and the Penumbra System with Separator 3D group. A binomial comparison will be used to test the one-sided null hypothesis that the difference in proportions is less than or equal to -0.15 ($H_0: P_{3D} - P_{Control} \leq -0.15$) vs. the alternative ($H_1: P_{3D} - P_{Control} > -0.15$). This is equivalent to evaluating that the lower bound of the 90% confidence interval for the difference is above 15%. The primary effectiveness analysis will be performed on the Per Protocol (PP) subject population. The analysis based on the Intent-To-Treat (ITT) population will be considered as supportive.

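### The per-protocol set alone decides non-inferiority, but the plan does not say whether device failures treated with cleared rescue stay in it, or which TICI reading counts for them in either set

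*SAP*

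**What the plan says.** **Deciding set.** SAP 2 rests study success on the primary non-inferiority criterion and names no population. SAP 9.1 supplies it: "The primary effectiveness analysis will be performed on the Per Protocol (PP) subject population", and "The analysis based on the Intent-To-Treat (ITT) population will be considered as supportive". Protocol 9.2 lists ITT and PP without ranking them.

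**Membership.** Under SAP 5.1, "only patients who actually received the assigned treatment and do not have major protocol violations will be included". Neither document says what makes a violation major. Protocol 3.9 covers the patient in whom the assigned system did not reach TIMI/TICI 2 or 3: "use of other rescue therapies are considered a protocol deviation and must be reported in the Case Report Forms". It does not grade that deviation. Protocol 3.4 adds deviations that differ by arm: 041 or 054 separators in the 3D arm, and the Separator 3D in control.

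**Scoring.** The failure rule in SAP 9.1 starts "For those patients who are treated with IA tPA or other non-FDA-approved treatments for the purpose of reducing the clot burden" and sets these patients to TICI 0 to 1 for the primary analysis. No such rule covers other rescue. Protocol 3.8 asks for scores after the Separator 3D step, around each further Penumbra component and around adjunctive treatment, then says: "The TIMI/TICI scores after the use of the Penumbra System as well as after adjunctive treatments will be used for analysis". Protocol 3.9 adds that "TIMI/TICI scores must be recorded before and after the use of rescue therapy". Protocol 2.2.1 places the endpoint straight after the procedure. Protocol 4.2 frames effectiveness as what the system itself achieves.

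**Knowledge of arm.** SAP 3.4: "The Penumbra Inc. clinical team responsible for the conduct of the study, the investigator, and center study personnel will not be blinded". Patients and the Core Lab are blinded.

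**The concern.** There are two separate gaps.

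1. *Population.* Under Protocol 3.9, rescue is a deviation precisely when the endpoint has been missed. If such a deviation is later graded major, a failure leaves the set that decides the trial. When failures leave both arms in the same proportion, the two observed rates move together and the margin becomes easier to meet. Unequal loss can push the error either way. ITT would show a conflict, but SAP 9.1 gives it no say.

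2. *Scoring.* If cleared rescue opens the vessel, the pre-rescue and final readings differ and the plan does not choose between them. This affects ITT as much as PP, so changing the primary population would not cure it.

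The exposure is mainly cleared rescue. The SAP 9.1 failure rule would do nothing in a PP analysis that had already removed the IA tPA and non-approved cases, so it implies that they remain as failures. I treat a product marketed under FDA clearance as outside that rule; the Protocol introduction uses clearance and approval interchangeably for the Penumbra System.

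**Working it through.** **Plan's own figure.** Inputs from Protocol 9.1 and SAP 3.2: 80% in both arms, margin 15%, one-sided alpha 0.05, power 85%.

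n = (1.645 + 1.036)² × (0.8×0.2 + 0.8×0.2) / 0.15² = 7.19 × 0.32 / 0.0225 = 102.2, so 103 per arm. Power at 103 is 0.852, as printed. 103/0.9 = 114.4, so 115. No stated number is disputed.

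**Decision rule.** SAP 3.1: the one-sided 95% normal-approximation lower bound for 3D minus control must exceed −15%.

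**One data set, three readings of the plan** (assumed counts, 115 per arm; 84 3D and 92 control successes before rescue; 8 of 31 and 6 of 23 failures rescued, 26% in each arm):

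| Handling of rescued failures | 3D | Control | Difference | Lower bound | Margin met |
|---|---|---|---|---|---|
| Kept as failures | 84/115 | 92/115 | −7.0% | −16.1% | no |
| Dropped from PP | 84/107 | 92/109 | −5.9% | −14.6% | yes |
| Counted as successes | 92/115 | 98/115 | −5.2% | −13.4% | yes |

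First row: SE = √(0.730×0.270/115 + 0.8×0.2/115) = 0.0557; −0.0696 − 1.645×0.0557 = −0.161.

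**False non-inferiority at the margin.** True pre-rescue rates 65% and 80%, 115 per arm. With nothing dropped or converted the error is 5.0%. Single-set figures come from exact binomial enumeration, and joint-rule figures from 1,000,000 simulated trials. All dropping and conversion shares are assumptions.

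*Dropping a share r of failures from PP in both arms:* p′ = p / [p + (1−p)(1−r)]. For r = 0.2: 3D 0.65/0.93 = 69.9%, control 0.80/0.96 = 83.3%, difference −13.4 points.

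*The same, with 10% of successes also leaving:* p′ = 0.9p / [0.9p + (1−p)(1−r)]. For r = 0.1 the rates return to 65% and 80%. For r = 0.2 they are 0.585/0.865 = 67.6% and 0.72/0.88 = 81.8%.

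*Converting a share c of failures by cleared rescue:* p′ = p + (1−p)c. The true difference becomes −15(1−c) points; for c = 0.2 that is 72% against 84%, or −12.

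| Share of failures (r or c) | 10% | 20% | 30% |
|---|---|---|---|
| Dropped from PP | 6.5% | 8.6% | 12% |
| Dropped, and 10% of successes leave | about 5% | about 6.6% | about 9% |
| Converted (ITT and PP alike; device-only question) | 8.5% | 14% | 23% |

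*Unequal dropping:* 30% of failures in 3D and 10% in control gives 28%; the reverse gives 1.6%.

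*Requiring both ITT and PP:* about 4.3-4.5% under equal dropping, 5.0% at 30%/10% and 1.5% in the reverse. Under conversion of 10/20/30%, with 10% of the remaining failures also dropped, the joint error is still 7.6/13/21%.

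*If final TICI is the intended endpoint:* the error at that endpoint's own margin is 5.0% to 5.5% for control rates of 80% to 90%, so there is no inflation.

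**The case against.** A PP-led analysis is defensible in non-inferiority, and ITT is reported beside it. A rescued patient did receive the assigned treatment, and Protocol 3.9 speaks of a deviation while SAP 5.1 removes only major violations, so a sensible team may well keep that patient. These points stand.

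The dropping model removes failures only. Separator deviations under Protocol 3.4 can also occur in successes, and allowing for that lowers the figures, as shown. Choosing the pre-rescue reading also settles which question the trial answers. The documents require that a reading be named; which one is a judgement, for which Protocol 4.2 gives a reason. Nor can all violations be graded blind to arm and outcome, because some are defined by arm and rescue is defined by failure. A list written in advance is the workable safeguard.

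A reader might infer more than the documents support:

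- *That the plan removes rescued failures from PP.* It does not say so. They may leave.
- *That the error rate is inflated whatever endpoint is meant.* Conversion inflates it only for the device-only question.
- *That the pre-rescue angiogram never reaches the Core Lab.* Protocol 3.8 mentions pre- and post-procedure angiograms, but the Protocol synopsis and SAP 13.2 give the Core Lab all imaging scans. This needs confirming; it is not shown to be missing.
- *That Protocol 3.4 and 3.6.10 conflict beyond doubt.* The explicit exception in 3.4 may govern the general wording of 3.6.10. The text should say so.

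**Conclusion.** The point holds and should be fixed before database lock. PP decides alone, its exclusion criterion is undefined, and cleared rescue after device failure has neither a retention rule nor a named TICI reading. Making PP primary is not in itself the fault.

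The text is certain; the size is not. Equal dropping of 10-30% of failures moves a nominal 5.0% error to between about 5% and 12%, depending on whether successes leave too. For the device-only question, converting 10-30% of failures moves it to 8.5-23% in both sets. If final TICI is intended the error holds, but the aim in Protocol 4.2 goes unanswered. These figures assume true rates of 65% and 80%, 115 per arm and equal shares in the two arms. The worked example shows that the unwritten rules can reverse the conclusion on plausible counts; it does not show that they will.

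**What to change.** **(a) SAP 9.1 and Protocol 3.8.** In both sets, make the primary TICI the blinded Core Lab reading after the last Penumbra System component allowed in the assigned arm and before any non-Penumbra rescue. Keep the existing failure rule. Report final TICI as a sensitivity analysis. Confirm that the pre-rescue run goes to the Core Lab.

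**(b) SAP 5.1.** List the major violations before database lock and before any review of outcome by arm. State that rescue after the assigned device was tried is not a ground for exclusion from PP.

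**(c) SAP 2 and 9.1.** Declare success only if the lower bound exceeds −15% in both ITT and PP. This controls dropping but not conversion, so (a) is needed as well.

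**(d) Protocol 3.4 and 3.6.10.** Reconcile the two on 041/054 separator use in the 3D arm before such use is graded. No clinical rule is proposed.

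**Cost.** Wording, and at most one further Core Lab reading per rescued patient, since scores before and after rescue must already be recorded. Power:

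| Case | 115 per arm | 103 evaluable per arm |
|---|---|---|
| 80% in both arms, single set | 0.89 | 0.85 |
| 80%, both sets, 10-30% of failures dropped equally | 0.87 | 0.83 |
| 80%, both sets, 10% dropped in 3D and 30% in control | 0.74 | 0.70 |
| 3D 77%, control 80%, single set | 0.72 | 0.68 |

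The last row applies if pre-rescue scoring lowers only the 3D rate. If (b) makes the two sets nearly coincide, the joint rule keeps close to single-set power. The sample size should be rechecked if PP exclusions plus attrition are expected to exceed the planned 10%.

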9.2 Secondary Effectiveness Analysis

The secondary effectiveness variables:

- Good clinical outcome at 30 days post-procedure. Patients meeting one of the following are evaluated as having good clinical outcome: 10 points or more improvement in the NIHSS at Discharge; a NIHSS score of 0-1 at Discharge; 30-day mRS score of 0-2.

- Good neurological outcome at 90 days post-procedure. Patients meeting one of the following are evaluated as having a good neurological outcome at 90 days:
 - mRS score ≤ 2 at 90 days
 - mRS score at 90 days equal to the pre-stroke mRS score (if the pre-stroke mRS score was higher than 2)
 - 10 or more points improvement on the NIHSS score at 90 days
- The proportion of patients with a modified Rankin Scale (mRS) of ≤ 2 at 90 days post procedure.

Frequency counts and percentage of patients within each category will be provided for categorical data. Estimates of the treatment differences and their 95% confidence intervals will be calculated. Subject rates will be compared between treatment groups with Fisher's exact test.

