2.2 Study Objectives/Endpoints

The purpose of this study is to assess the safety and effectiveness of the Separator 3D as a component of the Penumbra System in the revascularization of patients presenting with acute ischemic stroke secondary to intracranial large vessel (≥ 2.5 mm in diameter) occlusion.

2.2.1 The primary endpoints are:

- Angiographic revascularization of the occluded target vessel at immediate post-procedure as defined by a TICI score of 2 or 3
- Incidence of device-related and procedure-related serious adverse event within 24 hours post-procedure

2.2.2 The secondary endpoints are:

- Good clinical outcome at 30 days post-procedure as defined by a 10 points or more improvement in the NIHSS at Discharge, a NIHSS score of 0-1 at Discharge; or a 30-day mRS score of 0-2.
- The proportion of patients with a modified Rankin Scale (mRS) score of ≤ 2 at 90 days post procedure.
- Good neurological outcome at 90 days post-procedure as defined by an mRS score of ≤ 2 , or equal to the pre-stroke mRS score if the pre-stroke mRS score was higher than 2, or an 10 or more points improvement on the NIHSS score.
- All cause mortality
- Incidence of symptomatic intracranial hemorrhage

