3.10 Post-Procedure Evaluations

All patients will be assessed for 90 days from time of procedure.

A follow-up noncontrast CT scan will be performed at 24±12 hours after procedure, and will be reviewed to assess hemorrhagic transformation based on ECASS definitions^{21,22}:

- HI 1 (small petechiae along the margins of the infarcted area without space-occupying effect),

- HI 2 (more confluent petechiae within the infarcted area but without space-occupying effect),
- PH 1 (hematoma in $\leq 30\%$ of the infarcted area with some slight space-occupying effect),
- PH 2 (hematoma in $>30\%$ of infarcted area with substantial space-occupying effect).

In addition, any neurological deterioration should be evaluated by urgent CT scan and other evaluations as indicated according to investigator/hospital best practice.

A symptomatic intracranial hemorrhage will be defined as 24 \pm 12 hour CT evidence of an ECASS defined ICH and a 4-point or more worsening of the NIHSS score.

Patients will be evaluated for neurological and/or functional status immediately post-procedure, 7 days after procedure (or day of discharge from the hospital, whichever is earlier), 30 days (± 10 days), and 90 days (± 10 days) after procedure. The assessments shown in **Table 7** must be performed:

Table 7 – Schedule of Assessments

Assessment	Pre-Admission Evaluation	Baseline Evaluation	Immediate Post-Procedure	24 \pm 12 Hr Follow-Up	7 days Follow-Up or Discharge ^D	30 Days Follow-Up (± 10 days)	90 Days Follow-Up (± 10 Days)
History		√					
Physical Exam ^A		√			√	√	√
NCCT ^B		√		√			
TIMI/TICI Scores from Angiography ^C		√	√				
NIHSS		√		√	√	√	√
mRS	√	√				√	√
Lipids Profile					√		
Liver Enzymes		√			√		
BUN, Creatinine		√			√	√	
CBC/Platelets/INR/PT/PTT		√	√		√	√	
Pregnancy Test		√					
Adverse Events			√	√	√	√	√

A: Includes recording of supine blood pressure and heart rate

B: In addition to the evaluation at Admission, standard CT scans must be obtained within 24 \pm 12 hours post-procedure and immediately after any neurologic decline that occurs within 90-day follow-up

C: From digital subtracted angiography

D: Assessments can be done either at 7 days from procedure or at Discharge, whichever occurs sooner.

4. Assessment of Safety and Effectiveness

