9.3.2 Secondary Effectiveness Endpoints

The secondary effectiveness variables:

- Good clinical outcome at 30 days post-procedure. Patients meeting one of the following are evaluated as having good clinical outcome: 10 points or more improvement in the NIHSS at Discharge; a NIHSS score of 0-1 at Discharge; 30-day mRS score of 0-2.
- Good neurological outcome at 90 days post-procedure. Patients meeting one of the following are evaluated as have a good neurological outcome at 90 days:
 - mRS score ≤ 2 at 90 days
 - mRS score at 90 days equal to the pre-stroke mRS score (if the pre-stroke mRS score was higher than 2)
 - 10 or more points improvement on the NIHSS score at 90 days
- The proportion of patients with a modified Rankin Scale (mRS) of ≤ 2 at 90 days post procedure.

Frequency counts and percentage of patients within each category will be provided for categorical data. Estimates of the treatment differences and their 95% confidence intervals will be calculated. Patient rates will be compared between treatment groups with Fisher's exact test.

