11.4 Modified Rankin Scale

0	No Symptoms
1	No significant disability, despite symptoms; able to perform all usual duties and activities
2	Slight disability; unable to perform all previous activities but able to look after own affairs without assistance
3	Moderate disability; requires some help, but able to walk without assistance
4	Moderately severe disability; unable to walk without assistance and unable to attend to own bodily needs without assistance
5	Severe disability; bedridden; incontinent, and requires constant nursing care and attention

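### As written, the secondary 30-day good clinical outcome can be met on the Discharge NIHSS alone, so some patients who die before day 30 count as good outcomes

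*SAP*

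**What the plan says.** Four places define the endpoint, all in the same way: the protocol synopsis, protocol 2.2.2, protocol 9.3.2 and SAP 9.2.

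- Protocol 2.2.2 opens with "Good clinical outcome at 30 days post-procedure as defined by a 10 points or more improvement in the NIHSS at Discharge" and joins the remaining criteria with an 'or'.
- Protocol 9.3.2 makes the either/or rule explicit ("Patients meeting one of the following are evaluated as having good clinical outcome") and lists "10 points or more improvement in the NIHSS at Discharge; a NIHSS score of 0-1 at Discharge; 30-day mRS score of 0-2".
- SAP 9.2 repeats the rule: "Patients meeting one of the following are evaluated as having good clinical outcome: 10 points or more improvement in the NIHSS at Discharge", followed by "a NIHSS score of 0-1 at Discharge; 30-day mRS score of 0-2".

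On timing, note D to Table 7 in protocol 3.10 says of the day-7/discharge visit: "Assessments can be done either at 7 days from procedure or at Discharge, whichever occurs sooner". The later visits are at "30 days (± 10 days), and 90 days (± 10 days) after procedure".

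Both analysis sections compare the arms on this endpoint with a 95% confidence interval and Fisher's exact test. Protocol 9.3.3 and SAP 9.4 use it again in the subgroup analyses. SAP section 2 states that secondary endpoints and subgroups do not decide study success or product claims.

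**The concern.** The label promises a status at 30 days, but two of the three sufficient criteria are settled at about day 7 or earlier, and nothing that happens later can reverse them. Take a patient who gains 10 NIHSS points by day 5 and dies on day 20. That patient meets the first criterion and, under the rule as written, is a good clinical outcome at 30 days.

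The plan does not merely leave a detail open here. Applied literally, the stated rule gives a result that contradicts the endpoint's name. What is at stake is the meaning of one named secondary effectiveness result and of the subgroup results built on it. If the rule stays silent, a programmer who notices the problem will have to decide it later, and SAP 3.4 says that the sponsor's clinical team and the investigators are not blinded.

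**Working it through.** **1. The plan's own figure.** No rate, power or sample size is stated for this endpoint. The only design figure is for the primary TICI endpoint, and it reproduces: (1.645 + 1.036)² × 2 × 0.80 × 0.20 / 0.15² = 102.2, rounded up to 103 per group; 103/0.90 = 114.4, rounded up to 115. It does not bear on this point beyond supplying the arm size.

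**2. When each criterion is read.**

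| Criterion | Read at | Requires survival to day 30? |
|---|---|---|
| NIHSS improvement of 10 or more | Discharge visit (day 7 or discharge, whichever is sooner) | No |
| NIHSS 0–1 | Discharge visit | No |
| mRS 0–2 | 30-day visit, window days 20–40 | Only to the visit, which may fall before day 30 |

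The result does not depend on how Discharge is read. Under note D, a patient still in hospital at day 7 can qualify and later die in hospital. If Discharge means the actual date of leaving, a death between that date and day 30 has the same effect.

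**3. Does any other text close the gap?**

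- *mRS scale (protocol 11.4).* The last printed grade is "Severe disability; bedridden; incontinent, and requires constant nursing care and attention", grade 5; there is no grade for death. Adding one would not be enough, because the NIHSS criterion has already been met.
- *Missing data (SAP section 12).* The baseline-score imputation applies to patients with no observation after randomization. A patient with a Discharge NIHSS has one. Death is not mentioned.
- *Deaths (protocol 9.4.2, SAP 10.5).* These rules serve the mortality analysis only.
- *Overrides.* SAP 9.1 writes an explicit failure rule for the primary endpoint (IA tPA or other non-approved clot-reducing treatment). SAP 9.2 has no counterpart for death.
- *The 90-day composite.* In SAP 9.2 its components are all tied to 90 days, so an early NIHSS gain alone does not qualify there.

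Nothing removes the patient described above from the successes.

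**4. Size.** One misclassified patient in an arm of 115 adds 1/115 = 0.87 points to that arm's rate. With 103 in the arm it is 1/103 = 0.97 points.

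The total needs two quantities that the documents do not give. Let d be the proportion of an arm that dies between the Discharge visit and day 30, and f the fraction of those who had met a Discharge NIHSS criterion. The inflation of that arm's rate is d × f, and the number of patients is 115 × d × f. Assumed values, for illustration only:

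| d | f | Inflation (points) | Patients per arm of 115 |
|---|---|---|---|
| 5% | 5% | 0.25 | 0.29 |
| 10% | 10% | 1.0 | 1.15 |
| 20% | 20% | 4.0 | 4.6 |

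If the arms contain a and b such patients, the between-arm difference moves by (a − b)/115. With 3 in each arm it does not move. With 3 more in one arm than in the other it moves by 3/115 = 2.61 points.

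**The case against.** The strongest reply is that this changes little, and much of that stands.

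- *Deaths are visible elsewhere.* A reader might infer that the rule hides late deaths. It does not hide them from the report. All-cause mortality is its own secondary endpoint, with Kaplan-Meier, log-rank and 90-day binary reporting by group (protocol 9.4.2; SAP 10.2 and 10.5). Only this one composite fails to penalise some of them.
- *No decision rests on it.* A reader might also infer a threat to the trial's conclusion. SAP section 2 excludes that, since success depends on TICI non-inferiority alone. SAP 9.3 also applies a Bonferroni correction to the secondary comparisons.
- *The number affected may be tiny.* Deaths before a Discharge NIHSS is recorded cannot qualify on it. No document says how many early improvers die by day 30. At the low end of the table it is less than one patient per arm. For scale, if success were 50% in each arm (assumed), the 95% half-width for the difference would be 1.96 × √(2 × 0.25/115) = 12.9 points.
- *An early-response component is a legitimate choice.* This is true, and the definition is the same in all four places. But crediting early improvement does not require crediting a patient who has since died, and neither document gives a reason for doing so under a 30-day label.

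These replies limit the consequence. None supplies a rule that makes death before day 30 a failure.

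**Conclusion.** The point holds as a defect in the definition of one secondary endpoint. Every patient who meets a Discharge NIHSS criterion and then dies before day 30 is counted as a 30-day good outcome, in the Fisher comparison and in the subgroup analyses.

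The effect is 0.87 points per such patient in an arm of 115. The total rests on assumed rates and runs from near zero to a few points; under the assumptions above, 0.25 to 4.0. The documents support neither a specific bias within that range nor a direction favouring either arm. A shift of several points in the treatment difference would require nearly all such deaths to fall in one arm. The primary conclusion, the mortality analysis and the sample size are unaffected. The change is worth making because the rule is wrong for every patient it touches and the correction costs almost nothing.

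**What to change.** In the protocol synopsis, protocol 2.2.2, protocol 9.3.2 and SAP 9.2, add: *A patient who dies on or before calendar day 30 post-procedure is not a good clinical outcome, whatever the Discharge NIHSS or mRS.*

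The cut-off should be a fixed calendar day, not the 30-day visit. With a window of ±10 days, a patient who dies on day 33 without having attended has no visit date to compare against. SAP 10.5 already uses a fixed day for 90-day deaths. Naming the mRS as well covers a visit held from day 20 that is followed by death before day 30.

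Optionally, report a supportive version that replaces the Discharge NIHSS with the 30-day NIHSS already scheduled in Table 7.

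Cost: one sentence in four places, before the SAP sign-off that is due ahead of database lock. Deaths are already captured to day 90, so no new data are needed and the sample size does not change. The reported success rate may be slightly lower.
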